This study will be conducted at the Minneapolis Veterans Affairs Medical Center (MVAMC). The MVAMC is home to the Stroke Specialty Program (SSP), a CARF accredited program. The SSP tailors rehabilitation for survivors of any stroke mechanism (hemorrhagic, occlusive, etc.) affecting any part of the brain. Services can be adapted for survivors with cognitive challenges. The SSP has averaged 41 admissions in the past three years, though 2017 has projected admissions over 50. Retrospective chart review demonstrates the primary diagnosis resulting from stroke to be hemiplegia in approximately half of the admissions. Most patients (85%) are older than 60 years, predominantly Caucasian (85%) or African-American (10%) and male (98%).

Recruitment: Prospective participants will be screened by a clinician. Patients meeting study criteria will begin the consenting process. We will attempt to recruit twelve subjects each year for a sample of 24. Assuming 20% attrition by 3-month follow-up, we anticipate a sample of 20.

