The ability of this home-based model to revolutionize care delivery likely hinges on the extent to which it can be integrated into the inpatient setting. By initiating game-based treatment during the inpatient rehabilitation stay, patients and caregivers can become comfortable with the technology before they return home. Patients and families have told us that this exposure is essential, as they are often too overwhelmed during the transition-to-home period to pursue new approaches. In addition, inpatient staff that had not delivered a gaming intervention did not refer eligible individuals to a home-based gaming rehabilitation research program, despite weekly outreach by research staff.⁷² Qualitative data from patients indicating that they would be unlikely to seek new alternatives upon returning home and evidence of poor referral rates to a home-based gaming program suggests that a strong pipeline between inpatient and outpatient care is needed for adoption/penetration of tech-based approaches.

Discharging patients with the gaming system that they utilized during their inpatient stay would enable immediate access to unlimited rehabilitation upon returning home, reduce care disparities and likely reduce long-term care costs.⁷³ Moreover, the gaming system would already be optimally customized to each clientâ€TMs level of ability upon first in-home use. The proposed pipeline from inpatient to community treatment will therefore enable high-repetition in-home practice to therapist specification without requiring continued access to a therapist. It thus has the potential to improve outcomes and reduce care disparities. It may also help prevent secondary health complications (e.g., deconditioning, weight gain, frozen shoulder)⁷⁷ by encouraging increased mobilization post-discharge.

Lastly, this project responds to calls for greater access to care by improving the continuity of care for patients who incur stroke by extending active intervention from the acute phase of treatment through discharge and into home-based therapy. This model of care has the promise to improve long-term outcomes, increase quality of life and reduce cost of ongoing care.

1. Risks to Subjects

Human Subjects Involvement and Characteristics.

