Potential subjects will be referred to the PI or Study Coordinator (SC) by clinician members of the Study Team. The PI or the SC will meet with the potential subject to discuss the details of the study and to answer any questions that the Veteran has about study participation. If the potential participant meets all the inclusion criteria and none of the exclusion criteria an appointment for the initial visit will be made. At this visit, the informed consent process will begin, and consents will be obtained, including the Authorization for Use and Release of Individually Identifiable Health Information Collected for VHA Research will be obtained, and the Consent for Production and Use of Verbal or Written Statements, Photographs, Digital Images, and/or Video or Audio recordings by VA. The subject will be given ample time to ask questions, confer with family regarding participation in the research study, and to have questions answered. If the patient lacks decision-making capacity, the surrogate consent process will be employed with the patient and their Legally Authorized Representative/Personal Representative (described below in section 2).

Should the study coordinator not be able to meet with the participant in-person, consent may be done over the phone or via a VA approved teleconferencing system, with a study clinician available in-person to assist as needed. When consenting subjects via phone or teleconferencing system, all participants will have a physical copy of the consent/assent and HIPAA forms to be signed in wet ink. Copies of the singed consent/assent and HIPAA forms will be given to the participant, study records, and the IRB. A study clinician may be there in person to assist with the forms and technology set up. A wet in signature will be obtained before any study activities begin.

If the study coordinator or any research personnel are unable to interact with the participant in-person (e.g., due to the COVID-19 related administrative hold on research), in-person study visits may still take place with a study clinician only if the clinician is already seeing the inpatient clinically, as part of their regularly scheduled OT. All hospital mandated safety and PPE requirements will be followed.

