Personal questions, including demographic information will be asked on an initial questionnaire. Measures of impairment and quality of life will also be administered. Subjects will answer the questions in a quiet room; privacy will be considered and protected. There is a slight possibility of psychological risk if answering the questions causes a subject to become uncomfortable. These questions pose minimal social and legal risk.

Because CPRS will be accessed for recruitment, payment purposes, and for the writing of the Research Participant Progress notes, there is a minimal risk that private personal information can be accessed for fraudulent purposes.

Subjects may experience economic harm by participating in the study, such as additional transportation costs to travel to the facility and possible lost wages due to time missed from work once the participant is

an outpatient. The subject remuneration will be compensation for time and inconvenience. To minimize this potential harm, subjects will receive \$50.00 for each study visit.

2. Adequacy of Protection from Risk

Recruitment and Informed Consent. The potential study participant will meet with the Study Coordinator in the patientâ \in^{TM} s hospital room or other more private location if needed, or via phone/teleconferencing system. They will discuss the consent and HIPAA forms. Keeping in mind the subjectâ \in^{TM} s privacy, the coordinator will speak discreetly with the Veteran. A description of the study, the purpose of the study, the benefits and risks of participation, research subjectâ \in^{TM} s rights, disclosure of protected health information and the subjectâ \in^{TM} s right to confidentiality are among the items covered in the consenting process. The Study Coordinator will be up to date with all required trainings including CITI Training and VA Information Security.

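### Treated patients enter by study-team referral and control charts are picked by study-team clinicians; neither group follows a consecutive-case rule, so selection could bias the ARAT comparison unseen

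*Combined protocol and SAP*

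**What the plan says.** **Entry to the treated group.** Section 1 (Risks to Subjects) states: "Potential subjects will be referred to the PI or Study Coordinator (SC) by clinician members of the Study Team". Table 4 lists clinician referral as the first contact, and no other route is described. The Recruitment paragraph says "Prospective participants will be screened by a clinician". Section 2 (Recruitment and Informed Consent) puts the formal screening exam after consent, and Table 4 lists it in the same order.

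**Pool and target.** Setting of Research Study says: "The SSP has averaged 41 admissions in the past three years, though 2017 has projected admissions over 50". Hemiplegia is "the primary diagnosis resulting from stroke to be hemiplegia in approximately half of the admissions". The Recruitment paragraph adds: "We will attempt to recruit twelve subjects each year for a sample of 24".

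**Controls.** The Retrospective Chart Review paragraph uses charts from the past 5 years of inpatient stroke rehabilitation at the site. Study-team clinicians identify which charts. The paragraph does not say that Table 3 is applied to them, or how many there will be.

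**Analysis.** Statistical Analysis names mixed effects linear models or non-parametric equivalents for ARAT change. It mentions no matching or baseline adjustment. Its only selection check compares patients lost to follow-up with completers.

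**The concern.** Without randomisation, the ARAT comparison depends on how each group was assembled. A patient who is not referred never reaches the screening step, so the plan leaves no record of whether that patient was eligible. If referral goes with expected recovery, or with expected ability to manage the game, the treated group's ARAT change carries that prognosis as well as any treatment effect. The control patients passed no referral judgement for this game, but their charts pass through a clinician's choice of a different kind. Two unrecorded selections are then set against each other.

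The comparison matters even in a pilot, because the Future work paragraph and section 4 both say the study will establish initial efficacy. Missed referrals would also cost patients from a sample of only 24.

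**Working it through.** **1. The plan's own figures.** 12 × 2 = 24. After 20% attrition, 24 × 0.80 = 19.2, against 20 stated, so the figure reproduces to within one patient. The documents contain no power calculation, alpha, ARAT standard deviation or chart count.

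**2. Target as a share of the hemiplegia pool** (admissions read as per year, half with hemiplegia).
- 41 × 0.5 = 20.5, and 12 / 20.5 = 58.5%.
- 50 × 0.5 = 25, and 12 / 25 = 48%.

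**3. The same share on the plan's timeline.** Three preparatory months and recruitment completing by month 19 leave 16 months.
- Pool: 20.5 × 16/12 = 27.3, or 25 × 16/12 = 33.3.
- Share: 24 / 27.3 = 88%, or 24 / 33.3 = 72%.
- The stated pace of two to four per quarter gives 2 × 16/3 = 10.7 to 4 × 16/3 = 21.3 patients in that window, short of 24. Per year it gives 8 / 25 = 32% to 16 / 20.5 = 78%.

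**4. Illustration of what selection could do.** Suppose a share p of the pool enters by a normally distributed referral propensity that has correlation r with later ARAT change. With no treatment effect, the treated mean shifts by b = r × φ(z)/p standard deviations of change, where z cuts off the top share p. Assumptions not in the documents: r = 0.2 to 0.3, a two-sided 5% test, and 100 charts chosen without selection. Five years of hemiplegia admissions would be 5 × 20.5 = 102.5 to 5 × 25 = 125. With 24 treated, SE = √(1/24 + 1/100) = 0.227. The false-positive rate is 1 − Φ(1.96 − b/SE) + Φ(−1.96 − b/SE).

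| Share p | φ(z)/p | b at r = 0.2 | Rate | b at r = 0.3 | Rate |
|---|---|---|---|---|---|
| 48% | 0.83 | 0.17 | 11% | 0.25 | 19.5% |
| 58.5% | 0.67 | 0.13 | 9.0% | 0.20 | 14% |
| 72% | 0.47 | 0.09 | 7.0% | 0.14 | 9.5% |
| 88% | 0.23 | 0.05 | 5.5% | 0.07 | 6.1% |

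**5. Wider assumptions.** With r from 0.1 to 0.5, 20 treated and 20 to 125 charts, the rate is about 5.5% to 41% at shares of 48% to 59%, and about 5% to 16% at shares of 72% to 88%. The result depends mainly on r and p, and the documents fix neither.

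**The case against.** **A reader might infer that the plan's own background shows this route failing.** Relevance to the VA mission reports that "inpatient staff that had not delivered a gaming intervention did not refer eligible individuals to a home-based gaming rehabilitation research program". That concerns staff without gaming experience and referral to a home programme. Here the referrers belong to the study team, on the unit that delivers the game. The plan cites the episode as a reason for starting the game on the unit. It shows that inpatient staff can under-refer; it does not show that this route fails or that referral follows prognosis.

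**A reader might infer that clinicians choose which half of the hemiplegia patients is treated.** The 48% to 59% is a recruitment target over all hemiplegia admissions. Patients may also be missed because they have no arm function, live too far away, lack a TV or monitor, have a substance use or psychiatric exclusion, or decline. If only about half the pool is eligible and consents, nearly all of them must be referred to reach 12, and the modelled shift is close to zero.

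**The plan does tie entry to criteria.** The Recruitment paragraph says patients who meet criteria go on to consent, and Table 3 gives explicit therapist discretion only where it mentions tumor resection. That stands: discretionary referral is an inference from the absence of a rule. But those sentences govern patients already put forward, and none requires every admission to be considered.

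**The error rates rest on assumptions.** This also stands. They treat the charts as unselected, whereas study-team clinicians identify them too, so even the sign of the net bias is open.

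**This is a small single-site pilot**, study-team referral is ordinary practice in such work, and the definitive comparison is deferred. That limits the weight of the point, but a log is cheap and reasons for non-referral are hard to recover later.

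**Conclusion.** The concern holds as an unmeasured risk of selection bias on both sides of the ARAT comparison; it is not a demonstrated bias. It rests on four features of the plan: referral as the only described entry route, clinician-identified charts, no consecutive-case rule or log for either group, and no stated matching or baseline adjustment. The false-positive range of about 5.5% to 20% illustrates scale under the assumptions in step 4 of the working and should not be quoted as an estimate. The lower end belongs to the 88% share and the upper end to the 48% share. The plan should be changed on this point, but the point does not invalidate the pilot.

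**What to change.** **Treated group (section 1, referral sentence).** The study coordinator checks every Stroke Specialty Program admission against Table 3 each week in CPRS. Every patient who meets the criteria is approached unless the treating clinician records a reason. Clinician referral stays as an additional route, for example for inpatients outside that program.

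**Log.** Record each admission as eligible, approached and consented, with the reason where a step was not reached. Report the log beside the ARAT comparison.

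**Controls (Retrospective Chart Review).** Take all consecutive admissions in the 5-year window that meet the Table 3 criteria assessable from the chart, in place of a set identified by clinicians. List the criteria that cannot be assessed from charts.

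**Cost.** At 41 to 50 admissions a year, the check is about one chart a week (41/52 = 0.8 to 50/52 = 1.0), plus a rule for pulling control charts. CPRS access is already foreseen: "Because CPRS will be accessed for recruitment, payment purposes, and for the writing of the Research Participant Progress notes". The downside is a little coordinator time. Selection through consent remains, because the control patients were never asked; the report should state this as a limitation.

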Significant reform in the way that post-stroke care is delivered is needed. The standard for most inpatient rehabilitation facilities is 3 hours per day spent engaging in one-on-one therapeutic interventions with a therapist. Not only is this approach costly, but new literature partially erodes empirical support for this policy.³¹ A more distributed training approach involving frequent mobilization for shorter periods was associated with better health and function. Conversely more total hours spent in therapy had the opposite effect.^{7,8} Preference for distributed training is consistent with patient perspectives on the necessity of adequate rest during early rehabilitation and animal literature showing that very early intense motor training can be associated with deleterious effects on brain structure and motor function.³²⁻³⁴ Studies also suggest that there may be a critical time window of heightened neuroplasticity within the first few weeks post-stroke that may be bypassed if training does not emphasize neurorestoration (e.g., focuses exclusively on compensatory techniques) $^{35-40}$ and that increasing complex motor activity enhances neurorestoration.⁴¹⁻⁴⁷ Taken together, this literature indicates that frequent short-lived practice with the more affected upper extremity may convey the optimal benefit. Current care does not meet this standard well given that patients remain sedentary for much of the day^{48,49} and have limited opportunities for activity outside of therapy hours. The recommended distributed training approach cannot be easily employed within existing face-to-face treatment models of care due to staffing schedules (therapist tour 7:30-4 on weekdays) and increased documentation burden with distributed face-to-face treatment with a therapist. A potential solution to this problem is to supplement therapist care with technologies that can be utilized independently by patients during idle times of the day.

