
Participants will begin playing the Recovery Rapids game when clinically appropriate per the clinician, at least 1 week prior to discharge. We anticipate at least three sessions with an OT will be devoted to teaching the game and personalizing game play to the individual. Though the exact dosing schedule will be refined based on stakeholder feedback gathered during preparatory work, game play will then occur independently outside of OT/PT sessions. Study clinicians will determine how often participants should engage in the game, with a general recommendation being 10-minute periods three times per day with the possibility for more gameplay on weekends. Recreation therapy staff will assist participants with game setup as needed. Participants will be asked to track how much time they spend on the game. Study clinicians will engage in adherence strategies that are typically used clinically with the participant to enhance use of the gaming system as needed.

Participants will have the option of wearing smartwatches (Figure 3) on both upper extremities targeting a wearing schedule of: all waking hours during the inpatient stay and 3-month follow-up. An app on the smart-watch uses accelerometer hardware to record the number of movements performed. The app also enables notifications (vibration coupled with $\hat{a} \in \mathbb{C}$ Please use me $\hat{a} \in \mathbb{C}$ text prompt) if the arm is not utilized for a period of 10 minutes. Notification will be set to $\hat{a} \in \mathbb{C}$ for the weaker arm and $\hat{a} \in \mathbb{C}$ for the stronger arm.

Figure 3: Smart-watch Biofeedback device.

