discharge. Motor function will be assessed prior to treatment, before discharge, and at 3 monthsâ \in^{TM} follow-up by an OT. The primary outcome will be improvement on the Action Research Arm Test at post-treatment. The ARAT measures the time to complete standardized UE movements, with established reliability and validity. ⁶⁰⁻⁶³ Secondary measures of impairment, quality of life, and satisfaction with the gaming system may include the Wolf Motor Function Test (WMFT), Fugl-Meyer ⁶⁴⁻⁶⁷, Neuro-QoL⁶⁸⁻⁷⁰, and the Quebec User Evaluation of Satisfaction with assistive Technology (QUEST) respectively.

Statistical Analysis: Statistical analysis will be jointly led by our off-site collaborator [name] and the VA biostatistician. We plan to compare therapy induced changes in motor function (ARAT) and potentially motor impairment (Fugl Meyer), UE function (WMFT), and quality of life (Neuro-QoL) via mixed effects linear models or non-parametric equivalents will be used. We plan to examine outcome measure scores over time using graphical means. Statistical testing will be used to determine whether individuals lost to follow-up differ from those who completed the study.

Timeline: Institutional Review Board (IRB) review will be completed after funding is confirmed and before receipt of funding. Two-four patients per quarter will be recruited, with recruitment completing by month 19. The next 3 months will involve final follow-up data collection. The final 3 months will involve data analysis and publication preparation.

rable 2. Froposed Froject Ennemie								
Effect of Constraint-Induced Gaming Therapy in an			Q3	Q4	Q5	Q6	Q7	Q8
Acute Care Setting								
Participatory Action Research Methods								
Identify Ideal Implementation of Gaming CI Therapy								
Work with Tech Transfer								
Data Acquisition & Follow-up								
Data Processing and Analysis								
Annual and final reports to VA RR&D Service								
Dissemination of knowledge gained during the project								

Table 2. Proposed Project Timeline

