Patients meeting study criteria who consent to participate will be consented and enrolled in the study. Additional recruitment will be pursued if a participant chooses to leave the study prior to completion. Subjects will participate in the study while as inpatients at the Minneapolis VA and for up to 3 months post-discharge. Motor function for all subjects will be assessed prior to treatment (baseline), before discharge from the hospital, and at a 3-month follow-up appointment. A clinician Assessor-OT (A-OT) will conduct these assessments. Subjects will be compensated for their participation in the study in three \$50 disbursements: following the initial baseline assessment, following the assessments conducted at discharge, and following the 3-month follow-up appointment.

For all study participants, Occupational Therapy staff will conduct evaluations as usual that may include: Manual Muscle Testing (MMT), Range of Motion (ROM) measurements, and cognitive skills testing. They may also include many activities that are conducted at bedside, such as dressing, grooming, and showering. The subjects will be encouraged to participate in at least 3.5 hours of independent game play per week. Subjects will complete 1.5 hours/week dedicated to the $\hat{a}\in \mathbb{C}$ Transfer Package $\hat{a}\in \mathbb{C}$ during regular OT sessions. The other 3.5 hours of OT therapy will still be conducted and will bring total therapy time to 5 hours/week.

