Sources of Materials. Sources of material for this study will be subject interviews (e.g.-demographics and assessment instruments), existing computerized patient record system (CPRS) records, and data obtained from the research intervention itself (activity data collected by biofeedback devices). OT clinicians will write several types of notes in the medical record that will serve as a source of information for tracking usual care interventions and changes in health status for inpatient study participants. our OT evaluations (as usual) include MMT, ROM, Box and Block, Nine Hole Peg Test, and Action Research Arm Test (ARAT) The study coordinator will extract information from the OT Consult Note, OT Evaluation Note, OT Progress Note, the OT Discharge Note, and along with other information present in the medical record to capture differences in the rehabilitation treatments. For those in the outpatient setting, each subject will be given a study diary will contain a checklist to be used daily and will collect information including what interventions were used each day, and the intensity, duration and frequency for those interventions.

Potential outcome measures include the ARAT, Wolf Motor Function Test (WMFT), the Fugl-Meyer Assessment, the Neuro-QoL, and the QUEST 2.0.

During the study, arm use during daily activities (a potential moderator of improvement) will be tracked via a smart watch application. Participants will be encouraged to wear a smartwatch on each wrist during the inpatient stay and post-discharge until the 3-month follow-up visit.

Potential Risks. There is no therapeutic risk involved in the study. The risks associated with this study are research risks. The risks associated with the CI therapy in this research study are no greater than would be encountered in standard care. Research risks to the subjects include possible physical side effects from gaming. These physical risks include strained muscles and joints. The chance of these effects occurring is no greater than for gaming performed in daily life. Subjects will be encouraged to play for at least 10 minutes three times daily, thereby minimizing the risk of strain. There is a slight chance of these risks occurring.

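### The protocol states that there is no therapeutic risk, although its own background reports harm from more therapy hours; play is added to retained therapy, and no individual motor-worsening outcome is prespecified

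*Combined protocol and SAP*

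**What the plan says.** Under Potential Risks (section 1, Risks to Subjects) the protocol says "There is no therapeutic risk involved in the study", and adds: "The risks associated with the CI therapy in this research study are no greater than would be encountered in standard care". The only physical risk listed is muscle and joint strain. The other risks are discomfort with questions, privacy and economic loss. Strain is said to be kept low by encouraging a daily minimum of three ten-minute bouts.

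The opening background paragraph on reform of post-stroke care first associates distributed mobilization with better health and function, and then says: "Conversely more total hours spent in therapy had the opposite effect". It also cites animal literature in which "very early intense motor training can be associated with deleterious effects on brain structure and motor function". From this it concludes that "frequent short-lived practice with the more affected upper extremity may convey the optimal benefit".

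On exposure, Research Design and Methods says that "game play will then occur independently outside of OT/PT sessions". Human Subjects Involvement and Characteristics encourages at least 3.5 h of play a week, sets aside 1.5 h a week of OT for the Transfer Package, and adds: "The other 3.5 hours of OT therapy will still be conducted and will bring total therapy time to 5 hours/week". Table 1 gives about 30 inpatient hours of OT/PT and 10.5 h of encouraged inpatient play.

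On outcome, Approach to Aim 2 says: "The primary outcome will be improvement on the Action Research Arm Test at post-treatment". Statistical Analysis plans to compare changes in ARAT and to graph scores over time.

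**The concern.** The protocol relies on a body of evidence to choose its schedule, and then tells its readers that the risk described by that evidence does not exist. The sentence has consequences: under Recruitment and Informed Consent, risks are part of the consent discussion, and surrogate consent is allowed. The consent form itself is not available to this review, so nothing is said here about its wording.

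The pilot is also meant to inform a definitive trial of starting this treatment during the inpatient stay. If the report gives mean ARAT change and repeats that there is no therapeutic risk, it will not have examined case by case the one motor harm that the background raises.

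**Working it through.** **1. The two statements side by side.** The background makes two separate points. One concerns how practice is spread (short bouts are favoured). The other concerns total hours (more was worse). The trial follows the first by using ten-minute bouts. The second depends on whether total hours rise.

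**2. Do total hours rise?** Inputs are from Research Design and Methods, Table 1 and Human Subjects Involvement and Characteristics.
- Weekly play: 10 min × 3 per day × 7 days = 210 min = 3.5 h. This matches the stated 3.5 h.
- Three weeks: 3.5 × 3 = 10.5 h. This matches Table 1.
- Transfer Package: 1.5 h × 3 weeks = 4.5 h. This matches Table 1 and lies inside the OT hours.
- OT per week: 1.5 + 3.5 = 5 h, with play outside it.

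Play is therefore an addition. Over three weeks it adds 10.5 / 30 = 35%, for a total of 40.5 h. Play may start as late as one week before discharge. In that case it adds 3.5 / 30 = 11.7%, or about 12%. Both figures are encouraged hours, not delivered hours.

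**3. The stated protection against strain.** The protection offered is a minimum play time. A minimum does not cap exposure, so it cannot be what limits strain. Research Design and Methods also allows for more play at weekends.

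**4. What would show worsening?**
- ARAT is taken at baseline, before discharge and at 3 months. Change can be negative, and it is compared and graphed.
- Protection Against Risk provides clinical monitoring and asks participants to report unexpected changes. The five-business-day report to the IRB is for events that are unexpected, serious and related or probably related.
- The Data and Safety Monitoring Plan deals almost wholly with data security. The two-weekly calls are for watch use and compliance.
- No decline threshold, count of decliners or safety outcome is given.

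**5. What the sample can say.** The plan recruits 24 and expects 20 at 3 months after 20% attrition; 24 × 0.8 = 19.2, close to the stated 20. With no decliner among n, the exact one-sided 95% upper bound is 1 − 0.05^(1/n):
- n = 24: 1 − 0.05^(1/24) = 11.7%
- n = 20: 1 − 0.05^(1/20) = 13.9%

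If the true rate of harm were 5% (an assumption), the chance of seeing no case among 20 would be 0.95^20 = 36%.

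**6. Slower gain against the chart controls.** The documents give no alpha, SD or control-group size. I assume two-sided alpha 0.05, 80% power, 20 treated, and 20 to 102 controls. The upper figure reads the 41 admissions as yearly and takes half with hemiplegia: 41 × 5 × 0.5 ≈ 102. The detectable deficit is (1.96 + 0.84) × √(1/20 + 1/controls). That is 0.89 SD with 20 controls and 0.69 SD with 102. Only a large shortfall in mean gain would be found reliably.

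**The case against.** The strongest reply is that the background cites this literature in support of the schedule the trial uses. The intense-training evidence is from animals, the bouts are short, and whether findings on hours in therapy carry over to self-paced arm gaming depends on sources not available here. That stands as an argument for lower risk. It does not support a statement of no risk, and it leaves the point about total hours unanswered.

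The second reply is that safeguards exist. The start of play is left to clinical judgement, study clinicians set how often each participant plays, staff monitor participants, and OT notes track changes in health status. That also stands.

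A reader might go further and infer any of the following, none of which the documents support:
- **Only improvement is read out.** The word appears in the outcome definition, but the planned analysis compares and graphs change in both directions.
- **Spontaneous recovery will hide harm.** The documents do not say that most patients recover spontaneously in this period. For the time after discharge they say that function typically declines.
- **Play raises therapy by 70%.** That figure is 3.5 h on 5 h of OT alone. The background statement concerns total therapy hours, for which 35% is the relevant upper figure.

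A further fair criticism is that counting ARAT falls would miss harm that takes the form of slower gain. The fix therefore has to keep the signed comparison with chart controls beside the count.

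**Conclusion.** The contradiction between the risk section and the background is real and needs to be reconciled, as does the use of a minimum play time as the protection against strain. The added exposure is 12% to 35% of inpatient OT/PT hours, if encouraged play is completed and the stay provides about 30 h. Worsening would be recorded in the data, but no individual worsening outcome is prespecified. Even a clean result would leave rates of decline up to 11.7% (n = 24) or 13.9% (n = 20) compatible with the data. This does not show that the intervention is harmful or that participants are unmonitored. It shows that a statement of no therapeutic risk is not supported by the protocol and could not be established by a pilot of this size.

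**What to change.** 1. Replace the sentence on therapeutic risk with a statement that motor worsening or slower recovery from added early training is a possible, unquantified risk. Reconcile it with the background, and reconcile the strain sentence with the fact that it states a minimum. No dose, start time or clinical rule is proposed here.
2. Prespecify one ARAT decline threshold before data review. Report the number and percentage of participants who decline from baseline to discharge and from discharge to 3 months, with exact confidence limits. Give the number without a score at each visit, since participation can end at discharge.
3. List each decliner with logged play time and, where the chart gives it, days from stroke to first play.
4. For baseline to discharge, show declines and signed ARAT change beside chart controls who have both scores. Describe declines from discharge to 3 months without attributing them to play, because the protocol itself expects function to fall then.

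The cost is a wording change, a less favourable risk statement and one descriptive table. Most of the data are already to be collected, with three limits: play time is self-tracked, stroke date is not a named item in the chart extraction, and the protocol does not confirm that past charts hold ARAT at both admission and discharge.
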